All subjects will remain on study until death, progressive disease, unacceptable toxicity or withdrawal of consent. If the participant undergoes another surgery for presumed tumor progression but pathological findings are consistent with pseudoprogression (inflammation and necrosis rather than active tumor), the participant will deemed to not have had tumor progression and may continue treatment with nivolumab after review with the principal investigator.

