5.3 Treatment and Evaluation/ Observation Cycles

Blood draws are also performed within 2 days of each infusion. Screening/ Baseline lab results may be used for C1D1 if performed within 14 days of initial treatment. Hematology and blood chemistry panel results must be reviewed by an investigator prior to each infusion. After the maximum of 24 months of therapy, blood draws will only be performed with every clinical and radiographic assessment every 8 weeks.

Prior to each infusion every 2-3 weeks and beyond the initial 24 months every 8 weeks, patients will undergo physical examination, neurological exam, and KPS assessment. Response assessment by MRI or CT and FACT-BR quality of life questionnaires will be performed every 6 weeks for the initial 24 months of therapy and thereafter every 8 weeks. Targeted questioning will collect adverse events and concomitant medications.

To confirm objective response (OR), partial or complete response (see section 11.1 for definitions) by tumor measurements must be confirmed by repeat assessments performed ≥ 4 weeks after the criteria for response are first met. Progression should also be confirmed by repeat scans ≥ 4 weeks after progression first suspected on MRI or CT.

If the participant undergoes another surgery for presumed tumor progression, but pathological findings are consistent with pseudoprogression, the participant will be deemed to not have had tumor progression and may continue treatment with nivolumab after principal investigator review.

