If the participant undergoes another surgery for presumed tumor progression but pathological findings are consistent with pseudoprogression (inflammation and necrosis rather than active tumor), the participant will deemed to not have had tumor progression and may continue treatment with nivolumab after review with the principal investigator.

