11.3 Response/Progression Categories

The RANO Response Criteria will be used in this study as summarized below.

11.3.1 Complete response (CR).

All of the following criteria must be met:

- a. Complete disappearance of all enhancing measurable and non-measurable disease sustained for at least 8 weeks. In the absence of a confirming scan at least 4 weeks later, this scan will be considered only stable disease.
- b. No new lesions.
- c. All measurable and non-measurable lesions must be assessed using the same techniques as baseline.
- d. Participants must be on no steroids or on physiologic replacement doses only.
- e. Stable or improved clinically, for clinical signs and symptoms present at baseline and recorded to be disease related.
- f. Stable or improved non-enhancing (T2/FLAIR) lesions.

Non-measurable disease cannot have a complete response.

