11.3.2 Partial response (PR)

All of the following criteria must be met:

- a. Greater than or equal to 50% decrease compared to baseline in the sum of products of perpendicular diameters of all measurable enhancing lesions sustained for at least 8 weeks. In the absence of a confirming scan at least 4 weeks later, this scan will be considered only stable disease.
- b. No progression of non-measurable disease.
- c. No new lesions.
- d. All measurable and non-measurable lesions must be assessed using the same techniques as baseline.
- e. The steroid dose at the time of the scan evaluation should be no greater than the dose at time of baseline scan.
- f. Stable or improved non-enhancing (T2/FLAIR) lesions on same or lower dose of corticosteroids compared to baseline scan.
- g. Stable or improved, for clinical signs and symptoms present at baseline and recorded to be disease related clinically.

Non-measurable disease cannot have a partial response.

11.3.3 **Progressive disease (PD)**

Any of the following criterions must be met:

a. >25% increase in sum of the products of perpendicular diameters of enhancing

lesions (over best response or baseline if no decrease) on stable or increasing doses of corticosteroids and sustained for at least 8 weeks. In the absence of a confirming scan at least 4 weeks later, this scan will be considered only stable disease.

- b. Any new enhancing measurable lesion.
- c. Clear clinical deterioration not attributable to other causes apart from the tumor (e.g. seizures, medication side effects, complications of therapy, cerebrovascular events, infection, etc.). The definition of clinical deterioration is left to the discretion of the investigator, but it is recommended that a decline in the Karnofsky Performance Score (KPS) from 100 or 90 to 70 or less, a decline in KPS of at least 20 from 80 or less, or a decline in KPS from any baseline to 50 or less, for at least 7 days, be considered neurologic deterioration, unless attributable to co-morbid events or changes in corticosteroid dose.
- d. Failure to return for evaluation due to death or deteriorating condition.

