11.4 Methods for Evaluation of Disease

All measurements must be performed and recorded in metric notation using ruler, calipers, or digital measurement tools. All baseline measurement should be performed as close to initiation of treatment and never >4 weeks before the treatment.

The same method and technique of measurement should be used to characterize each identified and reported lesion at baseline and during follow-up. Imaging-based evaluation is preferred to evaluation by clinical examination unless the lesion(s) being followed cannot be imaged but are assessable by clinical exam.

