11.5 Evaluation of Best Response

The best overall response is the best response recorded from the treatment start until disease progression (using as reference for progressive disease the smallest measurements recorded since the treatment started). If a response recorded at one scheduled MRI does not persist at the next regular scheduled MRI, the response will still be recorded based on the prior scan, but will be designated as a non-sustained response. If the response is sustained, i.e. still present on the subsequent MRI at least four weeks later, it will be recorded as a sustained response, lasting until the time of tumor progression. Participants without measurable disease may only achieve SD or PD as their best "response."

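### The printed response rules do not stop a resection for presumed progression, read as pseudoprogression, from being scored as a CR or PR in the primary ORR

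*Combined protocol and SAP*

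**What the plan says.** Three sections of the protocol deal with surgery for presumed progression when pathology points to pseudoprogression. Section 5.8 says "the participant will deemed to not have had tumor progression and may continue treatment with nivolumab after review with the principal investigator". Section 5.3 says "the participant will be deemed to not have had tumor progression and may continue treatment with nivolumab after principal investigator review". Section 1.1 has the same provision, ending "may continue treatment with nivolumab after review with the principal investigator". All three settle whether the event is progression and whether nivolumab may go on. None mentions response.

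The response rules are in Section 11:

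- 11.5 sets the window: "The best overall response is the best response recorded from the treatment start until disease progression".
- 11.3.2 defines PR by "Greater than or equal to 50% decrease compared to baseline in the sum of products of perpendicular diameters of all measurable enhancing lesions".
- 11.3.1 defines CR by "Complete disappearance of all enhancing measurable and non-measurable disease sustained for at least 8 weeks".
- 11.4 places the baseline measurement close to treatment start and "never >4 weeks before the treatment".
- 11.2 mentions a surgical cavity only to set a minimum thickness of 3 mm for tumor measured around it.

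Section 13.2 counts a patient in the ORR when best overall response is CR or PR, with iRANO confirmation at least 4 weeks later. Section 13.1 sets a null of 14%, a target of 35%, 15 + 15 patients per arm, expansion with more than 2 responses in the first 15, and success at 7 or more of 30.

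**The concern.** Read together, these rules leave a route by which the surgeon's work enters the primary endpoint as drug effect. An enhancing lesion grows on treatment and is removed, and pathology shows necrosis and inflammation. The patient is deemed not to have progressed, so the response window stays open. Later scans are compared with the pre-treatment baseline, and the removed lesion registers as a fall or a disappearance. Repeating the scan 4 or more weeks later does not screen this out, because a removed lesion stays absent.

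The primary endpoint is a small count set against a fixed cutoff, so one patient can decide whether an arm expands or is called positive. The 14% null is a response rate for TTFields alone; a response produced by resection says nothing about what the combination adds to it.

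**Working it through.** **Step 1: follow the rules as printed.**

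| Question | Printed rule | Effect after a resection read as pseudoprogression |
|---|---|---|
| Has the patient progressed? | 1.1, 5.3, 5.8 | No |
| Is best response still open? | 11.5 | Yes, until progression |
| What is the reference for PR? | 11.3.2, 11.4 | Pre-treatment baseline; no reset |
| Does the cause of shrinkage matter? | 11.3.1, 11.3.2 | Not asked |
| Does the patient enter the ORR? | 13.2 | Yes, if evaluable for efficacy |

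No section ends response assessment at surgery, sets a post-operative reference for response, makes the patient non-evaluable, or excludes a resected lesion.

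**Step 2: what the resection must achieve.** PR needs a residual of at most 50% of the baseline sum of products. If the sum has grown to 1.25 times baseline, the residual must be at most 0.50/1.25 = 0.40 of the enlarged area, so at least 60% of it must be removed. The patient must also meet the conditions on steroids, clinical state, T2/FLAIR and new lesions, the confirmation at 4 or more weeks, and the 8-week wording in 11.3.1 and 11.3.2.

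**Step 3: reproduce the design.** With X ~ Bin(15, p) in stage 1, Y ~ Bin(15, p) in stage 2 and cutoff R:

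P(positive) = Σ over x = 3 to 15 of P(X = x) · P(Y ≥ R − x).

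I took stopping at 2 or fewer responses, because that reproduces the early-stopping figure in 13.5.

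| Quantity | Plan | Recomputed |
|---|---|---|
| Early stopping at 14% | 65% | P(X ≤ 2) = 0.648 |
| Power at 35% | 85% | 0.852 with R = 8; 0.905 with R = 7 |
| One-sided alpha at 14% | 0.05 | 0.0455 with R = 8; 0.0993 with R = 7 |

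The sample size, early stopping and power match a minimax design with R = 8. The written R = 7 does not hold 0.05. That is a separate point, so both cutoffs are shown below.

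**Step 4: add surgical responses.** Let k1 patients in stage 1 and k2 in stage 2 be non-responders scored as responders, with all others at p = 0.14. Then X ~ Bin(15 − k1, 0.14) and Y ~ Bin(15 − k2, 0.14). The arm continues if X + k1 ≥ 3 and succeeds if X + Y + k1 + k2 ≥ R. The documents give no value for k1 or k2; the assumed range is 0 to 2 per arm in total.

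| k1, k2 | R = 8 | R = 7 |
|---|---|---|
| 0, 0 | 0.0455 | 0.0993 |
| 1, 0 | 0.0973 | 0.1977 |
| 0, 1 | 0.0883 | 0.1673 |
| 1, 1 | 0.1784 | 0.3162 |
| 2, 0 | 0.1876 | 0.3472 |
| 0, 2 | 0.1541 | 0.2483 |

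Each such patient adds 1/30 = 3.3 percentage points to the arm's observed ORR. One in stage 1 lowers the chance of early stopping at 14% from 0.648 to P(Bin(14, 0.14) ≤ 1) = 0.86^14 + 14 × 0.14 × 0.86^13 = 0.121 + 0.276 = 0.397.

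**Step 5: an assumed rate in place of a certain patient.** If a share s of true non-responders is scored this way, p becomes 0.14 + 0.86s.

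| s | p | R = 8 | R = 7 |
|---|---|---|---|
| 1% | 0.1486 | 0.061 | 0.126 |
| 5% | 0.1830 | 0.157 | 0.265 |
| 10% | 0.2260 | 0.341 | 0.477 |

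**The case against.** The strongest reply is that this is an omission, not a decision to score surgery as response. The three surgery provisions are silent on response, and the primary ORR is by modified iRANO, which Section 11 names but does not print; 11.3 prints criteria headed RANO. The source criteria may deal with resected lesions, and that cannot be checked here. This stands, and it limits the point to the printed rules. Those rules nevertheless give neither a site nor the analyst any instruction to set a resected lesion aside.

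The hurdles are also real. The further surgery may be a biopsy or a limited debulking, and the conditions in step 2 would remove some operated patients. They narrow the route without closing it, since a stable patient with a large resection can meet all of them. A removed lesion might be placed under the unknown status in 11.3.5, but the text does not say so.

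A reader might infer three stronger things. First, that the trial expects to send such patients to surgery: the provision is written as a contingency, and 5.3 asks for a repeat scan to confirm suspected progression. Second, that the false-positive rate is in fact doubled: that needs a certain false responder, and with none the effect is nil. Third, that the error always favors the treatment: it can only add responses to the ORR, but 11.5 refers progression to the smallest measurement since treatment start. A small post-operative residual can therefore bring a later progression forward and count against PFS.

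**Conclusion.** The gap is real and narrow. As printed, the rules can score a large resection, read as pseudoprogression, as a confirmed response in the primary ORR. One such patient in an arm at the null would multiply the false-positive chance by about 1.7 to 2.1, depending on the stage and the cutoff. These sizes rest on an assumed count of 0 to 2 per arm and on stopping at 2 or fewer responses in stage 1. The figures at 7/30 also carry the separate cutoff error, so those at 8/30 are the fairer measure of this point alone.

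It should be fixed. The documents do not support calling it fatal to the design: the frequency is unknown and may be zero, and the primary criteria are not printed in full.

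**What to change.** Add to 11.5 and 13.2: for the primary ORR, a reduction produced by on-study resection of an enhancing lesion does not count as response. Best overall response for that patient is fixed from the pre-operative scans, the patient stays in the denominator, and all such patients are listed.

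Leave the progression and PFS rules unchanged. A new post-operative baseline for progression would conflict with the smallest-measurement reference in 11.5 whenever the residual is larger than an earlier nadir.

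Add a sensitivity analysis that counts later responses measured against the post-operative scan.

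The cost is a sentence in each section and one extra table; sample size, visits and treatment do not change. The downside is that a true later drug response in an operated patient is not counted in the primary ORR, which may lower it slightly; the sensitivity analysis shows by how much. The rule should be settled before responses are counted, because choosing it with one or two such patients already known could decide an arm's result.

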5.9 Duration of Follow Up

After documented progression each subject will be followed by telephone or medical record review for survival until they meet criteria for removal from study as per below.

5.10 Criteria for Taking a Participant Off Study

Participants will be removed from study when any of the following apply: lost to follow-up, withdrawal of consent, or death. The reason for taking a participant off study, and date the participant was removed, must be documented in the case report form (CRF).

Severe adverse events, availability of new adverse toxicology in animals, and financial difficulties due to withdrawal of funds may result in stopping the trial. The investigator or IRB may take such actions. If the trial is terminated for safety reasons, subjects will be notified immediately and assured that appropriate treatment and follow-up will be available. If an investigator terminates the trial, the investigator will inform the subjects and IRB about the reason for such action. Similar notifications will be sent by the IRB if it takes such an action.

The reason for taking a participant off study, and the date the participant was removed, must be documented in the clinical source documentation.

6. DOSING DELAYS/DOSE MODIFICATIONS

The descriptions and grading scales found in the revised NCI Common Terminology Criteria for Adverse Events (CTCAE) version 4.0 will be utilized for dose delays and dose modifications for nivolumab and ipilimumab.

Patients with Grade 3-4 scalp skin toxicity from NovoTTF200A (OptuneTM) application, should hold TTFields therapy until resolved to Grade ≤ 2 , then resume at same compliance goal of 75% or above. Interval maximal topical or systemic therapy advised. Repositioning of arrays is advised for any Grade ≤ 2 along with maximal medical therapy.

Adverse events (both non-serious and serious) associated with nivolumab and/or ipilimumab exposure may represent an immunologic etiology. These adverse events may occur shortly after the first dose or several months after the last dose of treatment. Immunotherapy must be withheld for drug-related toxicities and severe or life threatening toxicities. See Section 5.5.1 for supportive care guidelines, including use of corticosteroids.

Criteria for disrupting treatment, dose modification, or discontinuation for adverse events that are attributable to nivolumab or ipilimumab are listed below. After dose modifications are per the clinical judgment of the investigator and agreement of the subject, the treatment will be resumed according to the table below. Dose modification may not be required for adverse events that are clinically manageable.

Toxicity	Hold For Grade	Timing for Restarting Treatment	Treatment Discontinuation
Diarrhea/ Colitis	2-3	Toxicity resolves to Grade 0-1	Toxicity does not resolve within 12 weeks of last dose or inability to reduce corticosteroid to 10 mg or less of prednisone or equivalent per day within 12 weeks
	4	Permanently discontinue	Permanently discontinue
AST, ALT, or	2	Toxicity resolves to Grade 0-1	Toxicity does not resolve within 12 weeks of last dose
High Bili ru bin	3-4	Permanently discontinue (see exception below)	Permanently discontinue
Type 1 diabetes mellitus (new onset) or Hyperglycemia	T1DM or 3-4	Hold immunotherapy for new onset Type 1 diabetes mellitus or Grade 3-4 hyperglycemia associated with evidence of beta cell failure	Resume immunotherapy when patients are clinically and metabolically stable
Hypophysitis	2-4	Toxicity resolves to Grade 0-1. Therapy with immunotherapy can be continued while endocrine replacement therapy is instituted	Toxicity does not resolve within 12 weeks of last dose or inability to reduce corticosteroid to 10 mg or less of prednisone or equivalent per day within 12 weeks

Dose Modification Guidelines for Drug-Related Adverse Events

Toxicity	Hold For Grade	Timing for Restarting Treatment	Treatment Discontinuation
Hyperthyroidism	3	Toxicity resolves to Grade 0-1	Toxicity does not resolve within 12 weeks of last dose or inability to reduce corticosteroid to 10 mg or less of prednisone or equivalent per day within 12 weeks
	4	Permanently discontinue	Permanently discontinue
Hypothyroidism		Therapy with immunotherapy can be continued while thyroid replacement therapy is instituted	Therapy with immunotherapy can be continued while thyroid replacement therapy is instituted
Infusion Reaction	2ª	Toxicity resolves to Grade 0-1	Permanently discontinue if toxicity develops despite adequate premedication
	3-4	Permanently discontinue	Permanently discontinue
Pneumonitis	2	Toxicity resolves to Grade 0-1	Toxicity does not resolve within 12 weeks of last dose or inability to reduce corticosteroid to 10 mg or less of prednisone or equivalent per day within 12 weeks
	3-4	Permanently discontinue	Permanently discontinue
Renal Failure or Nephritis	2	Toxicity resolves to Grade 0-1	Toxicity does not resolve within 12 weeks of last dose or inability to reduce corticosteroid to 10 mg or less of prednisone or equivalent per day within 12 weeks
	3-4	Permanently discontinue	Permanently discontinue
All Other Drug- Related Toxicity ^b	3 or Severe	Toxicity resolves to Grade 0-1	Toxicity does not resolve within 12 weeks of last dose or inability to reduce corticosteroid to 10 mg or less of prednisone or equivalent per day within 12 weeks
	4	Permanently discontinue	Permanently discontinue

Note: Permanently discontinue for any severe or Grade 3 drug-related AE that recurs or any lifethreatening event.

^a If symptoms resolve within one hour of stopping drug infusion, the infusion may be restarted at 50% of the original infusion rate (e.g., from 100 mL/hr to 50 mL/hr). Otherwise dosing will be held until symptoms resolve and the subject should be premedicated for the next scheduled dose; Refer to Investigator's Brochure (IB) – Infusion Treatment Guidelines for further management details.

^b Patients with intolerable or persistent Grade 2 drug-related AE may hold study medication at physician discretion. Permanently discontinue study drug for persistent Grade 2 adverse reactions for which treatment with study drug has been held, that do not recover to Grade 0-1 within 12 weeks of the last dose

If a patient experiences other adverse events, or several adverse events and there are conflicting recommendations based on Grade, the investigator will use the lowest reduced the dose. Dose modifications will be made based on an adverse event that occurs during any time during a cycle.

Participants who experience an adverse event that requires a treatment delay or dose reduction should be monitored with appropriate laboratory testing or other clinical evaluation at least weekly until resolution; if the adverse event does not resolve within 12 weeks, the Investigator will determine the best course of action.

For holds for reasons other than treatment related toxicities, if the participant does not meet criteria to resume treatment within 6 weeks of the event precipitating the hold, the study agent(s) may be restarted, as long as there has been no significant evidence of disease progression (e.g., by clinical findings, symptoms, tumor markers) during the treatment interruption.

Dosing interruptions are permitted in the case of medical / surgical events or logistical reasons not related to study therapy (e.g., elective surgery, unrelated medical events, patient vacation, and/or holidays). Subjects should be placed back on study therapy within 3 weeks of the scheduled interruption, unless otherwise discussed with the Sponsor. The reason for interruption should be documented in the patient's study record.

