2.4.5 Safety Profile

Refer to the Investigator's Brochure (IB) for Pharmacokinetic data.

Most common adverse reactions ($\geq 20\%$) in patients treated with nivolumab as monotherapy, included fatigue, rash, musculoskeletal pain, pruritus, diarrhea, nausea, asthenia, cough, dyspnea, constipation, decreased appetite, back pain, arthralgia, upper respiratory tract infection, pyrexia. In combination with ipilimumab, the most common reactions were fatigue, rash, diarrhea, nausea, pyrexia, vomiting, and dyspnea.

Nivolumab should be withheld for moderate and permanently discontinued for any of the following serious or life-threatening adverse reactions: pneumonitis, colitis, hepatitis (transaminase or total bilirubin elevation), nephritis and renal dysfunction, hypophysitis, adrenal insufficiency, encephalitis, or infusion reactions.

Patients with prior allogeneic HSCT should be monitored for signs of hyperacute, grade 3-4 acute GVHD, steroid-requiring febrile syndrome, hepatic veno-occlusive disease, and other immunemediated adverse reactions. Transplant-related mortality has occurred. Nivolumab can cause fetal harm.

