2.5.4 Safety Profile

Refer to the Investigator's Brochure (IB) for Toxicity data.

Blockade of CTLA-4 by ipilimumab leads to T-cell activation, inflammatory adverse events, primarily involving the skin (dermatitis/pruritus), GI tract (diarrhea/colitis), liver (hepatitis), endocrine glands (e.g., hypophysitis and adrenal or thyroid abnormalities), and other less frequent organs (e.g., uveitis/episcleritis). Most occur from treatment onset, but few occur weeks to months after discontinuation. Most are reversible with dose modifications, interruptions or discontinuation. In rare cases, these inflammatory toxicities prove fatal.

Patients should be assessed for signs and symptoms of enterocolitis, dermatitis, neuropathy, and endocrinopathy. Comprehensive metabolic panels (including liver function, adrenocorticotropic hormone [ACTH] level, and thyroid function tests) should be evaluated at baseline and before each dose of ipilimumab. It is advised to rule-out alternative etiologies for any suspected inflammatory toxicity. In general, for severe inflammatory or life-threatening adverse effects, ipilimumab should be permanently discontinued and systematic high-dose corticosteroid initiated. For moderate immune-mediated toxicities, ipilimumab should be held or delayed, and moderate-dose corticosteroids considered.

Based on limited clinical experience, corticosteroids do not seem to limit anti-tumor response, e.g. disease control was maintained in subjects with objective responses who received corticosteroid administration for concomitant serious inflammatory AEs.

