5.8 Criteria for Taking a Participant off Protocol Therapy

Duration of therapy will depend on individual response, evidence of disease progression and tolerance. Treatment will be discontinued for clinical or radiographic progression of disease, intolerance despite dose modification (defined as NCI Common Terminology Criteria for Adverse Events (CTCAE) version 4.0 Grade 3 or 4 that does not return to Grade 1 or 2 after interruption or reduction of dose for 4 weeks), or patient withdrawal. A patient who experiences a dose-limiting toxicity (DLT) can remain on study at a reduced dose, if deemed by the physician to be safe and beneficial for the patient to continue.

In the absence of treatment delays due to adverse events, treatment may continue until one of the following criteria applies:

- Global deterioration of health-related symptoms (clinical progression),
- Confirmed radiographic disease progression,

- Intercurrent illness that prevents further administration of treatment,
- Unacceptable adverse event(s),
- Treatment interruption for more than 4 consecutive weeks due to intolerance despite appropriate dose modification,
- Participant decides to withdraw from the study, or
- General or specific changes in the participant's condition render the participant unacceptable for further treatment in the opinion of the treating investigator,
- Protocol non-compliance,
- Pregnancy,
- Lost to follow-up, or
- Study termination by Investigator, Institution or IRB.

If a patient does not return for a scheduled visit, every effort should be made to contact the patient. In any circumstance, every effort should be made to document patient outcome, if possible. The Investigator should inquire about the reason for withdrawal, request that all unused investigational product(s) be returned, request the patient to return for a final visit, if applicable, and advise follow-up with the patient regarding any unresolved adverse events.

If the patient withdraws from the trial and also withdraws consent for disclosure of future information, then no further evaluations should be performed and no additional data should be collected. The Investigator may retain and continue to use any data collected before such withdrawal of consent.

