Rule out non-inflammatory causes. If non-inflammatory cause, treat accordingly and continue I-O therapy. Evaluate with imaging

Investigator Brochure BMS-936558/MDX1106/ONO-4538

nivolumab

Hepatic Adverse Event Management Algorithm

Rule out non-inflammatory causes. If non-inflammatory cause, treat accordingly and continue I-O therapy. Consider imaging for obstruction

Patients on IV steroids may be switched to an equivalent dose of oral corticosteroids (e.g. prednisone) at start of tapering or earlier, once sustained clinical improvement is observed. Lower bioavailability of oral corticosteroids should be taken into account when switching to the equivalent dose of oral corticosteroids. *I-O therapy may be delayed rather than discontinued if AST/ALT < 8 x ULN or T.bili < 5 x ULN.

**The recommended starting dose for grade 4 hepatitis is 2 mg/kg/day methylprednisolone IV.

Investigator Brochure BMS-936558/MDX1106/ONO-4538

nivolumab

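### Section 6 contradicts itself on permanent discontinuation: its Note conflicts with the hypophysitis and diabetes/hyperglycemia rows, and the liver exception and reduced dose it relies on are not given

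*Combined protocol and SAP*

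**What the plan says.** Protocol Section 6 gives hold, restart and stop rules in a table by toxicity and grade. The Note below the table says: "Permanently discontinue for any severe or Grade 3 drug-related AE that recurs or any lifethreatening event". It names no exception.

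Two rows reach the highest grades without an immediate permanent stop:

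- **Hypophysitis, Grades 2-4.** Restart is tied to recovery to Grade 0-1, and the same cell adds: "Therapy with immunotherapy can be continued while endocrine replacement therapy is instituted". Discontinuation follows only if the event has not resolved, or steroids cannot be reduced, within 12 weeks.
- **New-onset type 1 diabetes or Grade 3-4 hyperglycemia.** The action is to hold. The discontinuation column then reads: "Resume immunotherapy when patients are clinically and metabolically stable".

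Four other texts bear on the same decision:

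- The Section 6 liver row for Grades 3-4: "Permanently discontinue (see exception below".
- The hepatic footnote in Appendix E: "I-O therapy may be delayed rather than discontinued if AST/ALT < 8 x ULN or T.bili < 5 x ULN".
- Section 5.8: "A patient who experiences a dose-limiting toxicity (DLT) can remain on study at a reduced dose", provided the physician judges it safe and beneficial.
- The Section 2 safety summaries. Section 2.4.5 says "Nivolumab should be withheld for moderate and permanently discontinued for any of the following serious or life-threatening adverse reactions", with colitis and hypophysitis in the list. Section 2.5.4 says, as a general rule, that "for severe inflammatory or life-threatening adverse effects, ipilimumab should be permanently discontinued".

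**The concern.** The question is whether a patient may be dosed again after a severe immune event, not how long a hold may last. If two passages in one section answer it differently, a site can follow the protocol and stop for good, while another follows it and re-exposes. Patients are registered institution by institution (Section 4), so nothing in the registration process would bring the sites into line.

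Two things are at stake. The first is patient safety. The second is the secondary objective on rates and reasons for discontinuing any component of therapy (Section 1.3): the recorded outcome would depend partly on which passage a site applied.

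**Working it through.** No arithmetic applies. The check sets the passages side by side.

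**1. Link between grade and severity.** The Note speaks of life-threatening events, while the rows speak of grades. The only place that equates Grade 4 with life-threatening is the infusion-reaction table in Section 5.5.1. Carrying that reading to other toxicities is an assumption.

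**2. Grade 4, row by row, under that assumption.**

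| Section 6 row | Grade 4 action in the row | Agrees with the Note? |
|---|---|---|
| Diarrhea/colitis | permanent stop | yes |
| AST, ALT, bilirubin | permanent stop, subject to an exception | yes, apart from the exception |
| Type 1 diabetes/hyperglycemia | hold, then resume when stable | **no** |
| Hypophysitis | hold then restart, or continue on replacement | **no** |
| Hyperthyroidism | permanent stop | yes |
| Hypothyroidism | no grade given; continue on replacement | no graded rule to compare |
| Infusion reaction | permanent stop | yes |
| Pneumonitis | permanent stop | yes |
| Renal | permanent stop | yes |
| All other | permanent stop | yes |

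Of ten rows, seven agree with the Note, two conflict, and one is ungraded (it would conflict only if an event were life-threatening).

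**3. Recurrent Grade 3.** The Note stops treatment permanently. The hypophysitis and diabetes/hyperglycemia rows restart or continue and make no distinction for recurrence. This limb is weaker, because a reader can take the Note as adding a condition that a row leaves out, as it must be read for colitis, hyperthyroidism and the residual row. It does not depend on the Grade 4 assumption.

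**4. Is there a tie-break?** Section 6 has one sentence on conflicting grade-based recommendations. It concerns other or multiple adverse events and answers with the lowest reduced dose, so it does not decide stop against restart. The endocrine algorithm in Appendix E sends delay, resumption and discontinuation back to the protocol.

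**5. Liver exception.** What follows the table is the Note, footnote a (restarting an interrupted infusion) and footnote b (persistent Grade 2 events). None is hepatic. The only candidate is the Appendix E footnote quoted above, which the row does not cite. The flowchart it belongs to is not readable in the public text, so the box and grade it modifies cannot be established.

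**6. Dose-limiting toxicity and reduced dose.** Section 5.8 relies on both terms, and Section 6 also refers to dose reduction. The documents define no dose-limiting toxicity and list no reduced level of either drug.

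**7. Background sections (lesser point).** Section 6 holds and restarts Grade 3 colitis. Sections 2.4.5 and 2.5.4 attach permanent discontinuation to serious or severe reactions without giving a grade. The wording does not match, but the mismatch lies between background text and the operative table.

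**The case against.** The strongest reply is that this is loose drafting which an investigator would resolve. The Note can be read as overriding the rows. Section 6 also leaves room for clinical judgment, and Sections 5.1 and 5.5.1 both send the reader to Section 6 for dose modification. Part of this stands. Those pointers favour Section 6 over the Section 2 summaries, which is why the colitis mismatch is only a lesser point. They do not help where the conflict lies inside Section 6, and no text says that the Note overrides.

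A reader might infer more than the documents support:

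- **That a patient must both stop for good and be re-dosed.** Only the diabetes/hyperglycemia row is directive. The hypophysitis continuation, the Appendix E delay and the Section 5.8 sentence are all permissive.
- **That a first Grade 3 colitis contradicts the Note.** It does not; the Note covers Grade 3 only on recurrence. The tension comes from ungraded background wording, and for ipilimumab that wording is expressly general.
- **That the liver row and Appendix E give opposite commands.** Appendix E describes itself as guidance, and the relevant flowchart is not readable. What can be shown is a pointer with nothing at its end.
- **That one or two patients per arm would be affected.** This would start from the 12% treatment-related discontinuation rate in Section 2.6.3. That rate comes from lung cancer cohorts on combination therapy and counts patients who discontinued, not severe events in the two conflicting rows. Arm A begins on nivolumab alone. No share for those rows is given anywhere.
- **That the primary response analysis is compromised.** An early stop could affect evaluability under Sections 11.1 and 13.2, but nothing shows that the response test or its boundaries would change.

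**Conclusion.** The point holds in a narrow form. Within Section 6, the Note conflicts with the hypophysitis and diabetes/hyperglycemia rows for life-threatening events and, less sharply, for recurrent Grade 3 events, and no precedence is stated. Separately, the liver exception is missing from where the table says it is, and the dose-limiting toxicity and reduced dose are undefined. The background sections should be aligned, but they are secondary.

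The life-threatening limb rests on reading Grade 4 as life-threatening beyond infusion reactions. The number of patients affected cannot be estimated from the documents. The case for acting rests on the possibility of opposite handling of a severe event and on the comparability of the discontinuation data.

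**What to change.** The sponsor should, in one amendment:

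1. reconcile the Note with the hypophysitis and the diabetes/hyperglycemia rows, covering Grade 4 and recurrence explicitly;
2. supply the hepatic exception or delete the pointer, and reconcile the row with Appendix E;
3. define or delete the dose-limiting toxicity and reduced-dose wording in Sections 5.8 and 6;
4. align Sections 2.4.5 and 2.5.4 with the reconciled text;
5. state which passage governs if any difference remains.

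Which action is clinically right for each toxicity and grade is for the sponsor's medical team; this review takes no view. The cost is an edit to text and table, with no added patients, visits or tests.
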